PI	Principal Investigator
PIS	Participant Information Sheet
PSWQ	Penn State Worry Questionnaire
QA	Quality Assurance
QC	Quality Control
REC	Research Ethics Committee
SAE	Serious Adverse Event
SDV	Source Data Verification
SOP	Standard Operating Procedure
TMF	Trial Master File
YSD	Yolk Sac

STUDY SUMMARY

STUDY OVERVIEW	
Full title	The Psychological Effects of Miscarriage Prediction Score: A Prospective Study
Objectives	Primary: Assess psychological effects of the miscarriage prediction model. Secondary: Evaluate patient acceptability.
Type of trial	A randomised, single-site trial in pregnant women with ongoing intrauterine pregnancies <12 weeks.
Trial design and methods	Prospective, non-blinded RCT at a single centre. HADS and PSWQ used to assess psychological impact at baseline and day 7.
Health condition(s) or problem(s) studied	Threatened miscarriage, psychological impact in early pregnancy.
Target sample size	372 participants (186 per arm, adjusted for consent/dropout).
Trial duration per participant:	7 days (from consent to follow-up psychological questionnaire).
Main inclusion/exclusion criteria:	Inclusion: Pregnant women >16 years with ongoing singleton intrauterine pregnancy <12 weeks. Exclusion: Non-English speakers, psychiatric treatment, multiple pregnancies, or planned terminations.
Statistical methodology and analysis:	Non-parametric Wilcoxon Mann-Whitney rank sum test. Powered at 80% to detect difference in psychological outcomes. Sample size estimated based on expected variance in HADS scores.
STUDY TIMELINES	
Study Duration/length	1 year
Expected Start Date	April 2026
End of Study definition and anticipated date	Final follow-up of last enrolled participant.
Key Study milestones	IRAS submission, ethics approval, first participant enrolment, data collection completion.
STORAGE of SAMPLES	
Data collected / Storage	PIA Viewpoint Database (King's College Hospital). Anonymised data stored securely on NHS OneDrive.

1 INTRODUCTION

Early pregnancy loss is common and often causes significant psychological distress.(1,2) Approximately 75% of women presenting with pelvic pain and/or vaginal bleeding in early pregnancy will have an ultrasound scan that shows an ongoing pregnancy with a heartbeat. A previous study at Kings developed a miscarriage prediction model so that we can give women their odds that the pregnancy will be ongoing following that scan, but the impact of predicting early pregnancy outcomes on psychological well-being in this situation remains unclear. This study will assess the short-term psychological impact and acceptability of using a miscarriage prediction model in clinical practice. (3)

2 BACKGROUND AND RATIONALE

EPU's provide care for women experiencing abdominal pain, vaginal bleeding, or seeking reassurance following previous pregnancy loss. These units aim not only to offer accurate diagnosis of early pregnancy outcomes by determining the location and viability of the pregnancy, but also aim to reassure women, provide emotional support, and counsel for possible outcomes. Miscarriage, occurring in 1 in 5 pregnancies, is defined by the Royal College of Obstetricians and Gynaecologists (RCOG) as pregnancy loss before 24 weeks and early pregnancy loss as before 13 weeks. (1,4–6)

Miscarriage Prediction Models

In recent years, several miscarriage prediction models have been created to aid in counselling and guide decisions regarding further early pregnancy ultrasound scans. Whilst some of these models have been validated, the understanding of their impact on psychological well-being and patient acceptability is not well understood.

Our retrospective study of 5,427 pregnancies demonstrated that our miscarriage prediction model which included maternal factors (ethnicity, smoking, age, bleeding history) alongside ultrasound markers significantly improved predictive accuracy (AUC = 0.88, CI 0.87–0.80). (7) A strength of this model, is the data for these maternal factors are routinely collected. However, prospective validation is required. Before conducting a large validation study (~1,800 patients), it is crucial to first assess whether the model improves psychological well-being and is acceptable to patients.

Psychological impact of early prediction models

Early pregnancy loss, including miscarriage and ectopic pregnancy, frequently causes profound psychological distress, with around 20% of women reporting moderate depression, 18–32% experiencing anxiety, and 25–39% showing symptoms of post-traumatic stress

disorder (PTSD) within 4–6 weeks of the loss.(8) While these rates typically resolve to baseline levels within a year, the psychological toll in the immediate aftermath can be significant.(8)

Threatened miscarriage, defined as vaginal bleeding with a closed cervix and no fetal loss, is also associated with heightened levels of depression and anxiety.(9) This raises important questions about the role of prediction models in mitigating or exacerbating such distress.

Research on the psychological impact of early pregnancy prediction models remains limited and inconclusive. For example, one prospective randomised controlled study found that progesterone testing significantly reduced anxiety among women with an uncertain early pregnancy diagnosis, with 82% of participants indicating they would opt for the test again.(10) In contrast, a separate single-centre randomised trial found no objective psychological benefit when a viability prediction score was provided to women with an intrauterine pregnancy of uncertain viability, although the majority still perceived it as being helpful.(11)

These conflicting findings underscore the need for further investigation. Our study seeks to address this gap by exploring our miscarriage prediction model psychological impact and acceptability among women whose pregnancies have been shown to be ongoing despite their symptoms.

3 OBJECTIVES

This study aims to evaluate the psychological effects (via HADS & PSWQ scores) and acceptability of the miscarriage prediction model among women attending the EPU.

3.1 Primary Objective

Primary: Assess the psychological effects of using the miscarriage prediction model

3.2 Secondary Objectives

Secondary: Evaluate patient acceptability of the predictive model

4 STUDY DESIGN

Study design

The Null Hypothesis:

Providing individuals with their miscarriage prediction score at the time of assessment has no significant impact on psychological distress, including anxiety, depression (HADS), and worry (PSWQ), compared to those who do not receive their score.

This is a prospective, two-arm, non blinded randomised controlled trial. It is a single-centre study taking place at King's College Hospital, Early Pregnancy Unit.

We will apply to the NHS Research Ethics committee and all the participants will be asked to give written consent.

Methods:

The inclusion criteria for this study include a singleton correctly sited intrauterine pregnancy with a visible fetal heartbeat less than 12 weeks gestational age. The patient should be over the age of 16. Exclusion criteria include multiple pregnancy, patients who intend to terminate their pregnancy, , patients who are being investigated or treated for a psychiatric condition or those who are non-English speaking.

Eligible patients who consent to take part in the study will be given an information leaflet and verbal explanation of the study.

At their appointment, the patients' demographic details, clinical history, ultrasound measurement and images will be documented on a computer database (PIA Foetal Database, Viewpoint Bildverarbeitung GmbH, Munich, Germany). For the purpose of this study the clinical data collected will include: maternal age, ethnicity, smoking status during pregnancy, parity and indication of presentation.

A transvaginal ultrasound scan will be performed by a Gynaecologists who is specifically trained in early pregnancy ultrasound. The purpose of the transvaginal ultrasound scan includes determining the location of pregnancy, the viability and where appropriate recording of number of embryos. This is done with measurement of CRL, FHR, GSD and YSD. Pregnancy dating is based on CRL of a live embryo. In pregnancies < 7 weeks the greatest length of the embryo is taken as the CRL as crown and rump are not clearly visualised. Beyond 7 weeks, the CRL is measured in sagittal section of the embryo whilst excluding the yolk sac. The fetal heart rate is calculated as beats per minute using the software of the ultrasound machine after measurement with electronic calipers of the distance between two heart waves on a frozen M-mode image. The GSD is calculated as the average of three perpendicular diameter with the calipers placed at the inner edges of the trophoblast. The YSD is calculated as the average of three perpendicular diameter with the calipers placed at the center of the yolk sac wall. This is all part of routine clinical care.

At the end of their appointment, participants will be asked to complete a baseline HADs score. The HADs score is a widely used screening tool used to assess psychological distress, including anxiety and depression in clinic settings. It is a self-rating patient reported outcome measure. Fourteen items are divided equally in two subscales for anxiety (HADS-A) and for depression (HADS-B). The ratings of the 14 items are summed to give a final score ranging from 0 to 42. The HADs score has been used frequently in pregnant populations.

The PSWQ is a 16-item self-report scale which is designed to measure the trait of worry in adults.

The patients will be asked how they would like to be contacted in 7 days to repeat the HADS and PSWQ score. We will enquire if they consent to being contacted via email, telephone or text message.

Women will be randomly allocated to either receive their miscarriage prediction score or to the control group who do not receive any intervention. Randomisation will be carried out by the means of a computer-generated random numbers. To prevent selection bias, allocation will be concealed, and a secure online system (REDCap) will assign patients automatically.

For the patients allocated to intervention, the clinician will then calculate their score but inputting the patient's data on to a excel spreadsheet which will calculate the patient miscarriage prediction score using the following equation:

$$Y = -2.382 + 0.052 \times \text{maternal age (years with decimals)} + 0.482 \text{ if Afro-Caribbean} - 0.341 \text{ if South Asian} + 0.393 \text{ if East Asian} - 0.073 \text{ if Mixed ethnic origin} + 0.213 \text{ if Parous} + 0.647 \text{ if Smoker} - 0.165 \text{ if Abdominal pain as indication of the scan} + 0.709 \text{ if Vaginal bleeding as indication of the scan} + 0.239 \text{ if previous miscarriage as indication of the scan} - 0.226 \text{ if previous ectopic pregnancy as indication of the scan} - 0.241 \times \text{CRL (mm)} - 0.036 \times \text{delta FHR (bpm)} - 0.178 \times \text{delta Gestational sac diameter (mm)} + 0.633 \times \text{delta Yolk sac diameter (mm)} - 0.005 \times (\text{CRL} \times \text{delta GSD}) + 0.038 \times (\text{CRL} \times \text{delta YSD}) - 0.003 (\text{delta FHR} \times \text{delta GSD}) + 0.104 \times (\text{delta GSD} \times \text{delta YSD})$$

The patients randomized to intervention will then receive their score on the same day and could choose to do so either face to face or over the telephone. The General Practitioner will be informed of the patient's participation in the study.

For both groups 7 days after their initial assessment a repeat HADS and PSWQ score will be performed. This will be sent to the patient as previously consented. The patient will be sent two questions about the acceptability of the

1. Did receiving the miscarriage prediction score help you feel more informed and prepared about your pregnancy outcome? *(Yes/No, with an optional text box for further explanation.)*
2. Would you recommend that other women in early pregnancy receive a miscarriage prediction score as part of their care? *(Yes/No, with an optional explanation.)*

The primary outcome will be the difference in HADS and PSWQ at 7 days between cases and controls.

A power calculation was conducted to determine the required sample size for assessing the psychological impact of providing an individual with their miscarriage prediction score at the time of assessment. Given the non-parametric nature of Hospital Anxiety and Depression (HADS) scores, the Wilcoxon Mann-Whitney rank sum test was chosen.

The study was calculated to have 80% power and to detect a probability shift of 0.362 with a 0.05 two-sided significance level. We estimated a 75% acceptance level and 20% dropout rate. Based on these parameters, an initial required sample size was calculated to be 104 participants per group, giving a total of 208 participants. After the adjustments for dropout rates and consent rates, this would equate to 186 participants per group and a total of 372 participants.

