7 ELIGIBILITY CRITERIA

7.1 Inclusion Criteria

In order to be eligible to participate in this study, an individual must meet all of the following criteria:

- Have capacity to understand the study and to provide signed and dated informed consent.
- Willing to comply with all study procedures and be available for the duration of the study including consenting to follow up of the pregnancy outcome by letter, phone or email according to individual preference.
- Age 16 years or over
- Single live ongoing intrauterine pregnancy less than 12 weeks gestation

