7.2 Exclusion Criteria

An individual who meets any of the following criteria will be excluded from participation in this study:

- Women with pregnancies of unknown location, ectopic pregnancies or early pregnancy prior to an embryo being seen or an embryo without a heartbeat.
- Multiple pregnancies
- Those undergoing assessment or treatment for a psychological condition by a psychiatrist
- Those who do not speak English or require a translator
- Women who have taken part in another clinical trial in the last 3 months.

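### Sections 4 and 5 disagree on when and for whom the prediction score is calculated, and eligibility does not require the sac measurements that the score needs

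*Protocol*

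**What the plan says.** **Timing of the calculation.** Section 4 describes REDCap allocation and then continues: "For the patients allocated to intervention, the clinician will then calculate their score". Section 5, under Screening (Day 0), lists use of the model to calculate risk as the step just before randomisation, with no restriction to an arm. There, only the giving of the score depends on allocation.

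**Inputs.** The equation in section 4 uses CRL and the deltas of FHR, GSD and YSD. Of the scan, section 4 says "This is done with measurement of CRL, FHR, GSD and YSD", and adds "This is all part of routine clinical care". Each sac diameter is an average over three planes; for the yolk sac, "The YSD is calculated as the average of three perpendicular diameter with the calipers placed at the center of the yolk sac wall".

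**Eligibility.** Section 7.1 asks for "Single live ongoing intrauterine pregnancy less than 12 weeks gestation". Section 7.2 excludes "Women with pregnancies of unknown location, ectopic pregnancies or early pregnancy prior to an embryo being seen or an embryo without a heartbeat". The shorter criteria in section 4 add only that a heartbeat is visible. None of these mentions a measured gestational sac or yolk sac, and the protocol has no rule for a woman whose score cannot be calculated.

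**The concern.** The eligibility criteria secure a live singleton embryo, so they make CRL and FHR obtainable. They do not secure the other two ultrasound inputs. A woman without one of them satisfies every criterion, yet the intervention cannot be delivered to her.

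When the gap is discovered then matters. If the score is attempted only after allocation and only in the intervention arm, as in section 4, the study team learns who is unscoreable in that arm alone. The trial is not blinded, and this knowledge depends on scan findings. Women kept in the analysis without a score weaken the contrast between arms. Women withdrawn or excluded for want of a score would be removed from one arm only, on a feature that may relate to prognosis and to anxiety. If the calculation comes before randomisation for everyone, neither problem need arise, but the protocol does not say consistently that it does.

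**Working it through.** **1. What the equation needs.** Delta GSD enters four terms: the main effect and the products with CRL, delta FHR and delta YSD. Delta YSD enters three: the main effect and the products with CRL and delta GSD. If either diameter is missing, Y cannot be computed.

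**2. Sections side by side.**

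| Question | Section 4 | Section 5 |
|---|---|---|
| When is the score calculated? | After allocation | Listed before randomisation |
| For whom? | Intervention arm | No restriction stated |
| What depends on allocation? | Calculating and giving the score | Giving the score |
| Is a calculable score a condition of randomisation? | No | No |

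In both sections the scan comes before randomisation, so missing measurements fall in both arms by chance. Under section 4 only their discovery is one-sided. Under section 5 they are discovered before allocation, but the woman has already been found eligible and has consented, and nothing says what follows.

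**3. Size of the dilution.** Let f be the share of intervention women without a score. The documents do not give f, so the values below are assumptions. Suppose these women are analysed as randomised and respond as controls do. The Mann-Whitney probability then becomes (1 − f)p + 0.5f, so its distance from 0.5 shrinks by the factor (1 − f). Required sample size varies with the inverse square of that distance, so it rises by 1/(1 − f)²:

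- f = 2%: 1/0.98² = 1.04
- f = 5%: 1/0.95² = 1.11
- f = 10%: 1/0.90² = 1.23

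With 186 women randomised to the intervention, 186 × f is about 4, 9 and 19 women.

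**4. Effect on power.** The plan's own figure was checked first. Section 4 states 80% power, a probability shift of 0.362, two-sided 0.05, and 104 per group. Noether's formula gives N = (1.960 + 0.842)² / (3 × (0.362 − 0.5)²) = 7.849 / 0.0571 = 137.4, or 69 per group, so 104 is not reproduced. That mismatch is a separate matter, but it means the power loss has to be shown in two ways. Both use 104 analysed per group and power = Φ(√(3 × 208) × |p − 0.5| × (1 − f) − 1.960):

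| f | p = 0.362 as stated | p = 0.388, for which 104 per group gives 80% |
|---|---|---|
| 0% | 93% | 80% |
| 2% | 92% | 78% |
| 5% | 91% | 76% |
| 10% | 87% | 71% |

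The value 0.388 is 0.5 − √(7.849/624).

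**The case against.** The case on the other side has several parts.

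- **Section 5 already places the calculation before randomisation.** This is true, and on that sequence there is no one-sided discovery. But section 4 says otherwise, in the fuller account of the procedure, and section 5 does not make a calculable score a condition of randomisation.
- **The measurements are routine and made by trained operators.** This stands as a reason to expect few unscoreable women. It does not guarantee that each diameter is obtained and recorded, and it is also why requiring them costs little.
- **The dilution is small.** If 0.362 is the true target, power at 104 per group stays above 80% even at f = 10%. This stands. It fails only if 104 was set for a smaller, unstated effect.
- **Handling in the analysis may belong to the statistical analysis plan, which is not shown.** Agreed for the analysis population. An analysis plan cannot, however, settle whether scoreability is known before allocation.

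Three stronger readings are tempting, and the documents do not support them. A reader might infer that unscoreable women arise only in the intervention arm; they do not, because the scan precedes randomisation. A reader might infer that the randomised comparison is biased; that requires such women to be dropped, which the protocol nowhere states. A reader might also infer that an empty spreadsheet cell would be read as zero and give a woman a badly wrong risk. The spreadsheet is not shown, and neither its handling of blanks, the expected diameters nor the definition of delta is given, so no figure for such an error can be supported.

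**Conclusion.** The point holds as a contradiction and a gap. Sections 4 and 5 cannot both describe when, and for whom, the score is calculated, and the eligibility criteria admit women to whom the intervention cannot be delivered. If section 4 is followed, such women are identified in the intervention arm alone, although they exist in both.

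Analysed as randomised, they cause dilution: a sample about 4%, 11% or 23% larger for the same power at assumed shares of 2%, 5% or 10%. One-sided exclusion is a possibility the protocol leaves open, not something it prescribes. The true share is unknown and may be small. This is an inexpensive improvement that protects the randomised comparison; it is not evidence that the comparison is already compromised.

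**What to change.** 1. Reconcile section 4 with section 5 so that both say the same thing: whether a score can be calculated is established for every woman before randomisation, and only disclosure of the score depends on the arm.
2. Add an inclusion line to section 7.1, for example: *CRL, FHR, GSD and YSD all measured and recorded at the Day 0 scan.*
3. Make these four fields mandatory in REDCap, so that allocation is not released until they are complete.

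The cost is a wording change in section 4, one inclusion line and four required fields for measurements that the protocol already calls routine. The downside is that the few women without these measurements are not enrolled, which narrows the study population slightly to women who can be scored.

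### Acceptability question 1 puts two attributes under one Yes/No and asks only about benefit, so its answers are hard to interpret

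*Protocol*

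**What the plan says.** Section 3.2 gives a single secondary objective: "Secondary: Evaluate patient acceptability of the predictive model". Section 4 introduces its only specified measure with the line "The patient will be sent two questions about the acceptability of the" and then lists two items.

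- Question 1: "Did receiving the miscarriage prediction score help you feel more informed and prepared about your pregnancy outcome". The response format is "Yes/No, with an optional text box for further explanation".
- Question 2: "Would you recommend that other women in early pregnancy receive a miscarriage prediction score as part of their care". This is also Yes/No with optional explanation.

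Section 5 places both at day 7, alongside the repeat HADS and PSWQ. Neither question is ranked above the other, and no acceptability threshold is set. Section 2 explains why the result matters. Before a prospective validation study of about 1,800 patients, "it is crucial to first assess whether the model improves psychological well-being and is acceptable to patients".

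**The concern.** This point is about how question 1 is worded for women who did receive a score. There are two faults.

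First, it asks about two attributes and allows one answer. The two can diverge: a woman told that her risk is high may feel well informed and not at all prepared. She must choose which half to answer, and the data will not show which she chose.

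Second, it runs in one direction. It asks whether the score helped. No is therefore the answer both for a woman whom the score left unchanged and for a woman whom it left feeling worse. Only the optional text box could separate them, and she need not use it.

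The exact wording stands in the protocol, so this is not a detail left to the statistical analysis plan, and no analysis can recover a distinction that the answers never recorded. At stake is the meaning of one of the two results that will inform the acceptability half of the decision on the validation study.

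**Working it through.** The protocol gives no target proportion, threshold or test for acceptability, so there is no stated figure to reproduce. What can be checked is how much a Yes/No answer to this item identifies. All percentages below are assumptions for illustration, except the sample size.

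**Two attributes, one answer.** Let *a* be the share who feel more informed and *b* the share who feel more prepared.

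- If women answer Yes only when both apply, the Yes share lies between max(0, *a* + *b* − 1) and min(*a*, *b*).
- If women answer Yes when either applies, it lies between max(*a*, *b*) and min(1, *a* + *b*).

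Take *a* = 0.85 and *b* = 0.50:

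- Both required: from 0.85 + 0.50 − 1 = 0.35 to 0.50, that is 35% to 50%.
- Either enough: from 0.85 to min(1, 1.35) = 1, that is 85% to 100%.

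With women reading the item differently, the Yes share could lie anywhere from 35% to 100% for the same underlying experience. If every woman who felt prepared also felt informed, the range narrows to 50% to 85%, but nothing in the protocol guarantees that.

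Taking *a* = 0.80 and *b* = 0.50 gives 30% to 50% and 80% to 100%, so the conclusion does not depend on the exact values.

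**One direction.** Let *y* be the share answering Yes, and suppose that women whom the score made feel worse answer No. The share made worse then lies between 0 and 1 − *y*.

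- *y* = 0.70: 0% to 30%.
- *y* = 0.50: 0% to 50%.

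The answer itself does not narrow these intervals.

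**Compared with sampling error.** The protocol's required number before inflation is 104 per group (section 4). With 104 answers and 70% Yes, the 95% half-width is 1.96 × √(0.70 × 0.30 / 104) = 0.088, about 9 percentage points. The 30-point uncertainty about the share made worse is larger than that, and more participants would not reduce it.

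**The case against.** The strongest case on the other side is that this is a small wording flaw in one of two items for a secondary objective, and that the trial can still produce an unfavourable result. That is right, and it limits the point. Several stronger readings are tempting, and the protocol does not support them.

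- *Acceptability cannot come out badly.* It can. No is allowed on question 1, and No to question 2 says directly that a woman would not recommend the score. Both have free text.
- *Question 1 is the main item.* The protocol ranks neither.
- *Distress caused by the score would go unseen.* HADS and PSWQ are compared between arms at day 7 as the primary outcome. Sections 14.5 and 15.2 provide for documenting distress, and section 15.3 makes distress attributable to the score a ground for pausing the study. These do not ask a woman how the score itself affected her, but they do measure distress.
- *Day 7 is too early, because the outcome is not yet known.* A woman can feel prepared for an outcome before it happens; that is what a prediction is for.
- *Women will say Yes whatever the effect.* Section 2 describes a trial of a viability score that found no objective psychological gain, "although the majority still perceived it as being helpful". That is one trial in a different population, its question wording is not in the protocol, and perceived helpfulness may be a genuine finding about acceptability.
- *The result should be comparable with the earlier progesterone trial,* reported "with 82% of participants indicating they would opt for the test again". The protocol plans no such comparison, and that was a different test in women with an uncertain diagnosis.

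None of this answers the two faults themselves. The item still joins two attributes, and its No still pools no effect with harm.

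**Conclusion.** The point holds as a wording flaw in question 1. A Yes or a No cannot be tied to either attribute, and a No does not distinguish a score that made no difference from one that made things worse unless the woman adds free text.

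The effect on interpretation is large for this one item: under the assumed shares, a Yes proportion anywhere from 35% to 100%, and at 70% Yes a share made worse anywhere from 0% to 30%. These figures show what the item leaves undetermined and do not forecast the result. The first range assumes that women differ in how they read the conjunction; the second assumes that women made worse answer No.

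The effect on the trial is modest. Question 2 stands, and the primary comparison is unaffected. The change is worth making because it is cheap and can only be made before the answers are collected.

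**What to change.** Replace question 1 with two items, one on feeling informed about the pregnancy and one on feeling prepared for what might happen. Give each the same balanced options: helped, made no difference, made it worse. Keep question 2 as it is.

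Optionally, add a question on whether the woman would choose to receive the score again. Longer rating scales or a new headline item would be a matter of preference and are not needed to cure the fault.

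The cost is a change to the ethics-approved day-7 questionnaire and under a minute more per participant. No extra visits, staff or participants are needed.

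### HADS and PSWQ are jointly the primary outcome under a single two-sided 0.05, with no rule for either, both or order, and the protocol conflicts on which scale it is powered for

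*Protocol*

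**What the plan says.** Section 4 (Study Design) defines the endpoint in one sentence: "The primary outcome will be the difference in HADS and PSWQ at 7 days between cases and controls". The null hypothesis in the same section is also single. It is that giving the score "has no significant impact on psychological distress, including anxiety, depression (HADS), and worry (PSWQ").

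The sample-size text in section 4 gives one test, one power and one significance level. For the test, "the Wilcoxon Mann-Whitney rank sum test was chosen", with the distribution of HADS scores as the reason. For the rest, "The study was calculated to have 80% power" and was meant "to detect a probability shift of 0.362 with a 0.05 two-sided significance level". The result is 104 per group before inflation and 186 per group after it.

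On the scale behind that size, the Study Summary says "Sample size estimated based on expected variance in HADS scores". Section 9 (Statistical Methods) says instead that the size was set for a meaningful difference in both HADS and PSWQ. No effect size or variance specific to PSWQ appears anywhere.

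Section 4 describes HADS as 14 items in two subscales that sum to a total of 0 to 42. Of the other instrument it says: "The PSWQ is a 16-item self-report scale which is designed to measure the trait of worry in adults".

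**The concern.** A primary outcome made of two scales needs a rule for what counts as a positive trial. The possible rules give different trials: either scale suffices, both are required, or one is tested before the other. The protocol fixes the two-scale outcome, the joint null and a single 0.05, and does not choose among them.

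The null covers both scales at once, so the natural reading is that a difference on either would reject it. Testing each scale at 0.05 would then exceed the stated error rate. A split result, with one scale significant and the other not, would have no agreed meaning. That matters here because section 2 makes the trial a step before a validation study of about 1,800 patients. It also cites earlier randomised studies with conflicting results, so a split result is plausible. The trial is not blinded and is analysed within the research team, so the deciding scale should be fixed before outcome data are seen.

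**Working it through.** **Inputs.** From section 4: two scales, two-sided alpha 0.05, power 80%, probability shift 0.362, 104 completers per group. The protocol gives no HADS-PSWQ correlation, so the correlation ρ between the two test statistics is an assumption, shown as a range.

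**Step 1. The plan's own figure.** Noether's formula for the rank-sum test with equal allocation is N = (z₀.₉₇₅ + z₀.₈₀)² / (3 × (p − 0.5)²). With p = 0.362, so |p − 0.5| = 0.138, N = (1.960 + 0.842)² / (3 × 0.138²) = 137.4, or 69 per group. The stated 104 is not reproduced. The power of 104 per group at that shift is Φ(√(3 × 208) × 0.138 − 1.960) = Φ(3.447 − 1.960) = Φ(1.487) = 93%. The mismatch is a separate matter. It is relevant here because per-scale power could be 80% (as stated) or 93% (as the stated inputs give), so step 3 uses both.

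**Step 2. Either scale counts.** Each scale is tested at 0.05. Familywise error is 1 − P(|Z₁| ≤ 1.96 and |Z₂| ≤ 1.96) for a bivariate normal pair with correlation ρ. At ρ = 0 this is 1 − 0.95² = 9.75%.

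| ρ (assumed) | Familywise error |
|---|---|
| 0 | 9.75% |
| 0.6 | 8.8% |
| 0.8 | 7.8% |

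**Step 3. Both scales required.** Type I error stays at or below 5%. Joint power is P(Z₁ < a and Z₂ < a), where a is the normal quantile of the per-scale power: 0.842 for 80% and 1.487 for 93%. The same shift on both scales is assumed.

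| ρ (assumed) | Joint power, 80% per scale | Joint power, 93% per scale |
|---|---|---|
| 0 | 64% | 87% |
| 0.4 | 68% | 88% |
| 0.6 | 70% | 89% |
| 0.8 | 73% | 90% |

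**Step 4. Which scale is powered.** The Study Summary ties the sample size to HADS variance, and section 4 justifies the test by HADS alone. Section 9 says the size serves both scales. With no PSWQ effect or variance stated, the section 9 claim has no visible basis, and the assumption in step 3 that PSWQ shares the 0.362 shift cannot be checked.

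**The case against.** The strongest reply is that a success rule and multiplicity handling are often left to a statistical analysis plan, which is not shown. No sentence says that each scale will be tested at an unadjusted 0.05; that figure appears only in the sample-size text. This stands in part. It is why the error rate above is conditional. It does not remove the point, because the protocol itself fixes the two-scale primary outcome, the joint null, the single alpha and the conflicting powering statements.

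Four stronger readings are tempting, and the document does not support them.

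- A reader might infer that the plan misstates its error rate. It states no success rule, so the rule is undefined, not wrong. Under a both-required rule alpha is not inflated.
- A reader might infer that a both-required rule must miss 80% power. That follows only if each scale has exactly 80%. On the stated shift and 104 completers per group, joint power is 87-90% if PSWQ has the same shift.
- The null names anxiety, depression and worry, so a reader might count three tests and get about 12% at a correlation of 0.6. No section plans separate subscale tests, and section 4 sums HADS to one total.
- A reader might treat the trait description of PSWQ as part of the error-rate problem. It has no bearing on error rate, and the document gives no figure on how PSWQ responds over 7 days. It is only a side reason for placing PSWQ second.

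Other rules would also be defensible, such as 0.025 per scale. At the stated shift, 104 completers would then have 88.6% power per scale. If 104 is truly the 80%-power size at 0.05, this falls to 71.2%.

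**Conclusion.** The concern holds in a conditional form. The protocol names two scales as one primary outcome under one null and one alpha, with no rule for either, both or order. If either suffices at 0.05 each, familywise error is about 8-10% (assumed correlations 0.8 to 0). If both are required, alpha is held and the cost is power. How much is lost depends on whether the stated 80% or the stated shift and group size are taken at face value, and on an unsupported assumption that PSWQ shares the HADS effect.

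The conflict over which scale the sample size covers does not depend on any of these assumptions; it is in the text. All correlations are assumptions.

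**What to change.** - Name HADS total (0-42) at day 7 as the sole primary outcome. It is the only scale to which the Study Summary and section 4 specifically tie the sample size and the test.
- Test PSWQ second, at two-sided 0.05, only if HADS is significant. This fixed sequence holds familywise error for the two scales at 5% and needs no extra participants for multiplicity.
- Report the HADS anxiety and depression subscales as supportive, with confidence intervals.
- Restate the null hypothesis for HADS total, and align the Study Summary, the sample-size text in section 4 and section 9 so that they name the same scale.

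The cost is protocol wording, to be settled before outcome data are examined. The downside is that PSWQ alone could not support a confirmatory claim. If the sponsor wants both scales to carry that weight, it should state a split-alpha or both-required rule and give a PSWQ effect size to power it. The base of 104 per group would have to be re-derived first.
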